3. STUDY DESIGN

3.1 DESCRIPTION OF THE STUDY

Study BO41423 is a multicenter, open-label, single-arm study designed to evaluate the safety, efficacy, pharmacokinetics, and pharmacodynamics of emicizumab in patients with mild or moderate hemophilia A without inhibitors against FVIII. Four loading doses of emicizumab 3 mg/kg will be administered subcutaneously QW for 4 weeks followed by patient preference of one of the following maintenance regimens: 1.5 mg/kg QW, 3 mg/kg Q2W, or 6 mg/kg Q4W. The three maintenance dose regimens have shown equivalent average steady-state exposure, and demonstrated consistent efficacy and safety, and are approved in several countries for the treatment of Hemophilia A with or without FVIII inhibitors. As patients with mild or moderate Hemophilia A have residual FVIII levels of ≥ 1%, it is of interest to collect safety data over a longer time period. Therefore, in this study, the observation time to primary analyses was extended to approximately 52 weeks compared with prior Phase III studies investigating emicizumab.

Approximately 70 patients of all age groups will be enrolled, approximately 20 patients with mild (FVIII level between >5% and <40%) and approximately 50 patients with moderate (FVIII level between \geq 1% and \leq 5%) hemophilia A, without FVIII inhibitors whose phenotype warrants prophylaxis.

Emicizumab—F. Hoffmann-La Roche Ltd 28/Protocol BO41423, Version 3

Patients (or their legally authorized representative herein referred to as patient[s]) will choose the preferred emicizumab maintenance regimen (1.5 mg/kg SC QW, 3 mg/kg SC Q2W, or 6 mg/kg SC Q4W) after consultation with his or her treating physician. The chosen regimen needs to be maintained throughout the study until completion of at least 52 weeks.

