Exploratory PD biomarkers and safety biomarkers will be collected within 24 hours but no later than 48 hours of a treated bleed.

Emicizumab—F. Hoffmann-La Roche Ltd 29/Protocol BO41423, Version 3

[figure not shown]
After 24 weeks on prophylactic emicizumab, patients with suboptimal bleed control will be offered the option to increase their dose to 3 mg/kg QW, with approval from the Medical Monitor, if the protocol-defined criteria of suboptimal response is met (see Section 4.3.2).

Interim data reviews may be performed at various timepoints (e.g., for regulatory submissions), and the primary analysis for all patients will be conducted after 50 patients with moderate hemophilia A have completed 52 weeks of emicizumab treatment, are lost to follow-up, or have withdrawn, whichever occurs first. The primary analysis will occur at the specified time regardless if no patients with mild hemophilia A are enrolled; however, enrollment will be left open for patients with mild hemophilia A in order to enroll approximately 20 such patients. The total number of patients in the study might slightly exceed 70 patients depending on the number of female patients enrolled. Ideally, at least 5 female patients will be enrolled. If these are not recruited within the pool of 70 patients, the enrollment will remain open until they are enrolled or until the cutoff date of primary analysis, whichever occurs sooner. Note that all patients will be included in the primary analysis irrespective of their follow-up time. After the primary analysis, patients will continue to receive emicizumab according to the Roche Policy on post study drug access until emicizumab is approved and accessible to patients commercially.

Patients who discontinue study drug prior to end of study will return to the clinic for a safety follow-up visit, 24 weeks after the last dose of study drug. Patients who complete or discontinue from the study will return to the clinic for a study completion/discontinuation visit (see Appendix 1 and Appendix 2).

Figure 1 presents an overview of the study design. The schedules of activities are provided in Appendix 1 and Appendix 2.

Figure 1 Study Schema

QW = once a week; Q2W = every 2 weeks; Q4W = every 4 weeks.

Note: Patients who discontinue study drug prior to end of study will return to the clinic for a safety follow-up visit 24 weeks after the final dose of study drug.

^a Interim data reviews may be performed at various timepoints.

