3.3.2 Rationale for Patient Population and Analysis Groups

This study will include patients of all ages with mild or moderate hemophilia A without inhibitors against FVIII who warrant FVIII prophylaxis. As it has been shown that primary prophylaxis is beneficial for patients with non-severe hemophilia A who present with more severe bleeding patterns and prophylactic replacement therapy is used by approximately 30% of patients with non-severe hemophilia A, the efficacy and safety of emicizumab prophylaxis in these patients will be evaluated. The majority of patients enrolled will be of moderate severity (approximately 50 patients) as bleeding phenotypes that warrant prophylaxis in patients with mild disease are rare. The cutoff date of the primary analysis will be the observation time of 52 weeks after the last patient with moderate disease has been enrolled to reduce the risk of significant timeline prolongation because of potential difficulties in recruiting patients with mild hemophilia A who warrant FVIII prophylaxis. The primary analysis will occur at the specified time regardless if no patients with mild hemophilia A are enrolled; however, enrollment will be left open for patients with mild hemophilia A in order to enroll approximately 20 such

Emicizumab—F. Hoffmann-La Roche Ltd 32/Protocol BO41423, Version 3

patients. Ideally, at least 5 female patients will be enrolled. If these are not recruited within the pool of 70 patients, the enrollment will remain open until they are enrolled or until the cutoff date of primary analysis, whichever occurs sooner. Note that all patients will be included in the primary analysis regardless of their follow-up time.

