4.3.2 Study Treatment Dosage, Administration, and Compliance

The treatment regimens are summarized in Section 3.1. The emicizumab dosing regimen to be tested is emicizumab 3 mg/kg SC QW for 4 weeks followed by a maintenance dose of either 1.5 mg/kg SC QW, 3 mg/kg SC Q2W, or 6 mg/kg SC Q4W.

All patients with suboptimal control of bleeding as defined by the protocol will be offered the option to increase their emicizumab maintenance dose to 3 mg/kg QW, with approval from the Medical Monitor. Suboptimal response is defined as follows:

• ≥2 qualifying bleeds within 24 weeks while on prophylactic emicizumab

A qualifying bleed is defined as spontaneous, verified by investigator (e.g., by imaging or physical examination), and occurring while on prophylactic emicizumab at steady state (after Week 5). If the investigator believes that a specific patient warrants dose escalation on the basis of a different reason, he or she may discuss the case with the Medical Monitor for consideration and potential approval.

An increase of the emicizumab dose to 3 mg/kg QW can occur at the next scheduled emicizumab administration of the initial regimen (i.e., 1 week from the last dose of a QW regimen, 2 weeks from the last dose of a Q2W regimen, and 4 weeks from the last dose of a Q4W regimen).

Emicizumab—F. Hoffmann-La Roche Ltd 38/Protocol BO41423, Version 3

Refer to the pharmacy manual for detailed instructions on drug preparation, storage, and administration.

Any cases of overdose, medication error, drug abuse, or drug misuse of study drug will be determined from emicizumab data entered into the electronic, handheld device (see Section 5.3.5.12 for details).

Patients will be observed for a minimum of 60 minutes after the first three doses as described in Section 3.1.

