4.4 CONCOMITANT THERAPY AND PROHIBITED THERAPY

Concomitant therapy consists of any medication (e.g., prescription drugs, over-the-counter drugs, vaccines, herbal or homeopathic remedies, nutritional supplements) used by a patient in addition to protocol-mandated treatment from 4 weeks prior to enrollment to the study completion/discontinuation visit. All such medications should be reported to the investigator and recorded on the Concomitant Medications eCRF. Medications taken to treat a bleed (e.g., FVIII) will be reported only via the BMQ, except for FVIII taken in the week prior to starting emicizumab by patients who will continue their prior FVIII prophylaxis until the second loading dose of emicizumab. For these patients only, FVIII treatment taken in the week prior to the first dose of emicizumab will be recorded on the *Hemophilia History Medication 7 Days Prior to Enrollment* eCRF page.

4.4.1 Permitted Therapy

Patients will be permitted to use the following concomitant drugs and therapies during the study:

- Regular FVIII prophylaxis may continue until the second emicizumab loading dose to avoid bleeds before adequate emicizumab levels are reached. Concomitant routine FVIII prophylaxis is otherwise not permissible during the study.
- For the treatment of breakthrough bleeds, FVIII should be used at the lowest dose
 expected to achieve hemostasis. Given that circulating emicizumab may increase
 patients' coagulation potential, the doses required to achieve hemostasis may be
 lower than FVIII doses used prior to the study.

Exact dose and schedule of FVIII should be discussed with patients at the beginning and throughout the study. Repeat dosing of VIII should be performed only under medical supervision and consideration should be given to verifying bleeds prior to repeated dosing.

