3.3.1 Efficacy Period

Efficacy period for each individual patient is defined as the number of days starting from the day of first emicizumab dose to the day of clinical cut-off or withdrawal from the study, whichever is earlier. For patients whose dose is up-titrated, the efficacy period ends a day prior to the first day on the up-titrated dose.

3.3.2 Efficacy Endpoints

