3.3.3 Subgroup Analyses

Additional descriptive summaries of both treated bleeds and all bleeds will be computed for various subgroups of the study. The summaries will include subgroup ABR and its 95% CIs. The main pre-specified subgroups are as follows:

- Age: 0 to <2, 2 to <6, 6 to <12, 12 to <18, 18 to <65, ≥65 years
- Race: Asian, Black or African American, White, Other
- Hemophilia severity: mild, moderate
- Number of target joints at study entry: no target joint, any target joint
- Previous treatment regimen: prior episodic, prior prophylactic
- Prior FVIII inhibitor: Yes/No
- Female patient: Yes/No
- Dosing regimens at enrolment: 1.5 mg/kg QW, 3 mg/kg Q2W, 6 mg/kg Q4W

Note that due to the likely small sample sizes, subgroup analyses will be highly susceptible to variability and should therefore be interpreted with caution.

Emicizumab —F. Hoffmann-La Roche Ltd 12/Statistical Analysis Plan BO41423 Additional region- and/or country-specific analyses may be performed to support regulatory submissions as needed.

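### The ABR clock starts at the first loading dose with no minimum follow-up, so severity, sex and interim-to-primary comparisons can carry a modest follow-up-dependent bias that no planned analysis would show

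*Protocol*

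**What the plan says.** **Clock.** SAP 3.3.1 counts the efficacy period "starting from the day of first emicizumab dose to the day of clinical cut-off or withdrawal from the study", whichever is earlier, and stops it the day before an up-titrated dose begins. SAP 3.3.2.1 uses this period as the model offset and as the denominator of the individual ABR. Protocol 6.5.1 uses the term in its formula without defining it.

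**Loading.** Under Protocol 3.1 every patient receives the same four weekly loading doses before the chosen maintenance schedule. Protocol 4.4.1 states: "Regular FVIII prophylaxis may continue until the second emicizumab loading dose to avoid bleeds before adequate emicizumab levels are reached." Protocol 4.3.2 counts a bleed towards suboptimal response only at steady state, which it places after Week 5.

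**Follow-up.** Protocol 3.1 sets no minimum: "Note that all patients will be included in the primary analysis irrespective of their follow-up time." Protocol 3.3.2 fixes the end: "The cutoff date of the primary analysis will be the observation time of 52 weeks after the last patient with moderate disease has been enrolled." Mild enrolment stays open to reach about 20 patients, with no closing date given. Enrolment of women can run up to the cut-off, but only if 5 have not been recruited within the 70.

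**Comparisons.** SAP 3.3.3 plans ABRs by severity, sex, previous treatment regimen and "Dosing regimens at enrolment: 1.5 mg/kg QW, 3 mg/kg Q2W, 6 mg/kg Q4W". SAP 2.5 and 3.9 plan an interim once the 50 moderate patients reach 24 weeks. No ABR that leaves out the loading phase is planned.

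**The concern.** A log-time offset removes the effect of follow-up length only when the bleed rate is the same throughout follow-up. Here the first four weeks differ from the rest in two ways. Emicizumab levels are still building up, which could raise the rate. Patients coming from prophylaxis may also have FVIII cover in the first week, which could lower it. A group with shorter follow-up gives those weeks more weight.

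Protocol 3.3.2 expects mild patients to be hard to recruit, so follow-up may well differ by severity, and possibly by sex. Severity and sex are pre-specified ABR subgroups in a single-arm, descriptive study. The interim also has shorter follow-up than the primary analysis. In each case two ABRs could differ although maintenance emicizumab works equally well in both. SAP 3.3.1 already removes time on an up-titrated dose at the end of the period, but it has no counterpart at the start.

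**Working it through.** The plan states no figure to reproduce: no loading-phase rate, no alpha or power, no interval width. The check is direct arithmetic.

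**Inputs from the documents.** Loading lasts 4 weeks. Cut-off is 52 weeks after the last moderate patient enrols. The interim follows 24 weeks of treatment. Total length is about 27 months, or 27 × 52.18/12 = 117 weeks.

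**Assumptions.** The loading-to-maintenance rate ratio r is 2 to 3 (r = 1 means no bias). Recruitment is uniform. Moderate recruitment lasts R = 61 weeks (117 − 4 screening − 52 treatment), or R = 37 weeks if 24 weeks of safety follow-up are also taken off.

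**1. Loading share by follow-up.** Share = 4/w for w weeks: 7.7% at 52, 16.7% at 24, 33% at 12, 50% at 8. Loading is the larger part only below 8 weeks.

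**2. Group shares at cut-off.**

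| Group | Mean follow-up (weeks) | Mean loading (weeks) | Share |
|---|---|---|---|
| Moderate, R = 37 | 52 + 18.5 = 70.5 | 4 | 5.7% |
| Moderate, R = 61 | 52 + 30.5 = 82.5 | 4 | 4.8% |
| Enrolled evenly over the last 52 weeks | 26 | (4 × 48 + 8)/52 = 3.85 | 14.8% |
| Enrolled evenly over the whole window, 89 or 113 weeks | 44.5 or 56.5 | 3.91 or 3.93 | 8.8% or 7.0% |

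In the third row, 8/52 = 15% of patients have under 8 weeks.

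**3. Late group against moderate.** With person-time weighting, a group's ABR relative to the maintenance rate is 1 + (r − 1) × share.

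- Late enrolment, r = 2: 1.148/1.057 = 1.09 (R = 37) and 1.148/1.048 = 1.09 (R = 61).
- Late enrolment, r = 3: 1.296/1.113 = 1.16 and 1.296/1.097 = 1.18.
- Whole-window enrolment: 1.088/1.057 = 1.03 and 1.070/1.048 = 1.02 for r = 2; 1.176/1.113 = 1.06 and 1.139/1.097 = 1.04 for r = 3.

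**4. Interim against primary, moderate patients.** Mean follow-up at the interim is 24 + R/2 = 42.5 or 54.5 weeks, so the shares are 9.4% or 7.3%. The ratios are 1.094/1.057 = 1.04 and 1.073/1.048 = 1.02 for r = 2, and 1.188/1.113 = 1.07 and 1.147/1.097 = 1.05 for r = 3.

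**5. Excess in the first week only.** For 12 against 52 weeks of follow-up: (1 + 1/12)/(1 + 1/52) = 1.06 for r = 2, and (1 + 2/12)/(1 + 2/52) = 1.12 for r = 3. If the excess lasts all four weeks, the same comparison gives 1.333/1.077 = 1.24 and 1.667/1.154 = 1.44.

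**6. Weighting.** The negative binomial model weights short follow-up more heavily than person-time does. A 4-week patient carries about 11% to 37% of the information of a 52-week patient (1 to 3 bleeds a year, dispersion 0.5 to 2, both assumed), against 7.7% of the time. The ratios in steps 3 and 4 are therefore approximate. The observed mean ABR, which becomes the sole method if the model does not converge, weights every patient equally. One bleed in 28 days gives 365.25/28 = 13.04, against 365.25/364 = 1.00 over 364 days.

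**The case against.** A reader might infer that each regimen's ABR is wrongly charged with four weeks before the regimen began. The documents do not support this. Protocol 4.3.2 defines the tested regimen as loading followed by maintenance, and loading is the same under all three schedules. It dilutes differences between regimens and does not by itself favour one.

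A reader might also infer that late mild and female patients are judged largely on loading-phase time. That needs under 8 weeks of follow-up. The 27-month expectation puts the last enrolment near week 61 after the first. If the last moderate patient enrols in week M, the latest entrant then has about M + 52 − 61 = M − 9 weeks at cut-off, so under 8 weeks requires all 50 moderate patients within about 17 weeks. Enrolment over the full 52 weeks before cut-off, as in the 1.09 to 1.18 scenario, would overrun that timeline. SAP Section 2 makes the timeline depend on recruitment, so this remains possible but is not the planned case. No section says that mild enrolment runs past the cut-off, and the extension for women is conditional.

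The rate ratio is assumed. Protocol 4.4.1 ties inadequate levels only to the time before the second loading dose, about one week, and the after-Week-5 marker governs up-titration, not efficacy. If the loading rate is higher, the Day 1 clock works against the drug. The study is descriptive, SAP 3.3.3 urges caution with subgroups, SAP 3.2 evaluates follow-up, bleeds are listed by patient, and a final analysis follows.

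Most of this stands and limits the size. It does not remove the point. The subgroup caution concerns small numbers, not a bias tied to follow-up. Follow-up is not stated to be reported by group. A conservative overall ABR does not make a between-group comparison fair. None of the planned summaries separates the loading weeks.

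**Conclusion.** The point holds as a cheap improvement, not as a flaw in the primary analysis. With no minimum follow-up and a clock that starts at the first loading dose, comparisons by severity and sex, and between interim and primary, can mix a follow-up effect with a treatment effect.

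On the assumption of 2 to 3 times the maintenance rate for all four weeks, the size is about 1.09 to 1.18 for a group enrolled evenly over the last 52 weeks, about 1.02 to 1.06 if enrolled evenly over the whole window, and about 1.02 to 1.07 for interim against primary. It is smaller if the excess lasts one week and zero if there is none. FVIII cover in prior-prophylaxis patients could reverse the direction. The documents settle neither the rate ratio nor the enrolment dates. That is a reason to show the supportive result, not to presume a bias.

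**What to change.** Keep the Day 1 ABR as primary. In SAP 3.3.1 add a supportive maintenance efficacy period that starts on the day of the first maintenance dose (Day 29) and ends by the existing rules. Report the ABR over that period beside the Day 1 ABR overall, by severity, by sex, by dosing regimen and at the interim. Give patient-years and follow-up for each group.

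The cost is SAP wording and one further model run per endpoint or subgroup, on data already collected. The supportive version drops 4/52, about 8%, of follow-up for a 52-week patient, and patients with 28 days or less do not contribute to it.

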3.2 END OF STUDY AND LENGTH OF STUDY

The end of this study is defined as the date when the last remaining patient has completed the last visit, as defined by the following criteria:

 Completion of at least 52 weeks of emicizumab treatment during the study and either transfers to commercially available emicizumab or receives further emicizumab per Roche Global Policy on Continued Access to Investigational Medicinal Products

OR

 Completion of the end of study safety follow-up visit 24 weeks after discontinuing emicizumab

OR

- Withdrawal of consent OR
- Lost to follow-up

In addition, the Sponsor may decide to terminate the study at any time.

The total length of the study, from screening of the first patient to the end of the study, is expected to be approximately 27 months.

The length of the study for an individual patient will include the following:

Screening period up to 4 weeks

Emicizumab—F. Hoffmann-La Roche Ltd 31/Protocol BO41423, Version 3

- Treatment period at least 52 weeks
- For patients who discontinue emicizumab, safety follow-up visit 24 weeks after discontinuation of emicizumab

3.3 RATIONALE FOR STUDY DESIGN

The Sponsor proposes a single-arm, multicenter, Phase III trial that will enroll patients of all ages with mild or moderate hemophilia A. The study will use approved dosing regimens at the choice of the patient following consultation with the treating physician. The study will assess the efficacy, safety, pharmacokinetics, and pharmacodynamics of emicizumab in patients with non-severe hemophilia A, as emicizumab has not been tested in patients without FVIII inhibitors with residual FVIII levels of $\geq 1\%$.

3.3.1 Rationale for Emicizumab Dose and Schedule

The three maintenance dose regimens have shown equivalent average steady-state exposure, and demonstrated consistent efficacy and safety, and are approved in several countries for the treatment of Hemophilia A with or without FVIII inhibitors. As patients with mild or moderate Hemophilia A have residual FVIII levels of $\geq 1\%$, it is of interest to collect safety data over a longer time period. Therefore, in this study, the observation time to primary analyses was extended to approximately 52 weeks compared with prior Phase III studies investigating emicizumab.

Patients in consultation with investigators will be allowed to choose the dosing regimen that is most appropriate for them as follows:

- Loading dose of 3 mg/kg SC QW ×4 weeks followed by one of the following:
 - Maintenance dose of 1.5 mg/kg SC QW
 - Maintenance dose of 3 mg/kg SC Q2W
 - Maintenance dose of 6 mg/kg SC Q4W

3.3.2 Rationale for Patient Population and Analysis Groups

This study will include patients of all ages with mild or moderate hemophilia A without inhibitors against FVIII who warrant FVIII prophylaxis. As it has been shown that primary prophylaxis is beneficial for patients with non-severe hemophilia A who present with more severe bleeding patterns and prophylactic replacement therapy is used by approximately 30% of patients with non-severe hemophilia A, the efficacy and safety of emicizumab prophylaxis in these patients will be evaluated. The majority of patients enrolled will be of moderate severity (approximately 50 patients) as bleeding phenotypes that warrant prophylaxis in patients with mild disease are rare. The cutoff date of the primary analysis will be the observation time of 52 weeks after the last patient with moderate disease has been enrolled to reduce the risk of significant timeline prolongation because of potential difficulties in recruiting patients with mild hemophilia A who warrant FVIII prophylaxis. The primary analysis will occur at the specified time regardless if no patients with mild hemophilia A are enrolled; however, enrollment will be left open for patients with mild hemophilia A in order to enroll approximately 20 such

Emicizumab—F. Hoffmann-La Roche Ltd 32/Protocol BO41423, Version 3

patients. Ideally, at least 5 female patients will be enrolled. If these are not recruited within the pool of 70 patients, the enrollment will remain open until they are enrolled or until the cutoff date of primary analysis, whichever occurs sooner. Note that all patients will be included in the primary analysis regardless of their follow-up time.

